### 9.2 Inventory and Accountability Records

All device shipments will have inventory and shipment records. Devices may be hand-carried to participating study sites by Study Sponsor personnel and will be accompanied by delivery of investigational device documentation (e.g. IFU, packing lists, transfer of investigational product form, etc.). The Investigator(s) or designee will take inventory of the product and complete the delivery documentation with receipt date and signature. Both the study site and the Study Sponsor will retain copies of these documents. The Investigator or designee will maintain a Device Accountability Log (as provided by the Sponsor) of all investigational devices documenting their receipt, disposition and return during this clinical study. The log will be kept with the documents for the clinical study and will be available for review during Study Sponsor monitoring visits. Only investigators trained and identified in the Delegation of Authority form on file at Edwards Lifesciences may use the investigational devices.

Use of the investigational devices and accessories provided for use in this study is prohibited outside of this protocol.

### 9.3 Device Storage

The device inventory will be stored in a locked, controlled, cool and dry area as described in the IFU and/or presented on the device labeling. This secured area will only be accessible to the Investigators or approved designee.

### 9.4 Device Return

The Investigator will receive instructions from the Sponsor on the return process (e.g. Sponsor request, study is terminated, or product expiration, etc.). All investigational devices must be returned to Edwards Lifesciences and the date of return must be recorded on the log. All unused devices in original package and/or those in opened packages as well as those removed from the

original package will be returned upon receipt of this notice. The Investigator's copy of the Device Accountability log must document any unused devices that have been returned.

Used devices may be handled and disposed of in the same manner as hospital waste and bio-hazardous materials in accordance with local regulations. There are no special risks related to the disposal of these devices. All returns and dispositions of devices will be captured on the Device Accountability Log.

## **10 DATA COLLECTION AND REPORTING**

The Sponsor will provide the study site with the clinical protocol, electronic case report forms, sample ICF(s), and all other necessary study-related documents. The Sponsor's Clinical Affairs Department, or designee, will conduct quality control and assurance of the study site, including but not limited to, data reviewing, data monitoring, and form collection. Every reasonable effort should be made to complete data entry in a timely manner.

### **10.1 Data Management**

Sponsor will provide data management through a secure, password protected Electronic Data Capture (EDC) system accessible via the internet.

### **10.2 Case Report Forms (CRFs)**

Electronic case report forms (eCRFs) will be used to collect patient data during the study. The Investigator, or an individual designated by the Investigator, is responsible for entering all data from the study onto the eCRFs hosted on a dedicated website. Electronic CRFs must be fully completed for each patient, and signed electronically by the investigator and/or designee. The eCRFs should be completed at the first earliest opportunity.

Data entered into the eCRFs may be subject to system validation checks (e.g. format range checks). System checks are automatic (i.e. generated at the time of data entry) and ensure the validity of submitted data. A query will be generated when a discrepancy requiring review has been identified. Discrepancies will remain open until a resolution is reached.

The site Investigator or designee must ensure the accuracy and completeness of the recorded data and then provide an electronic signature on the appropriate eCRFs. Changes to data previously submitted to the Sponsor will require a new electronic signature to acknowledge/approve the changes.

The Sponsor will conduct ongoing reviews of eCRF data. Sites that do not complete all data entry tasks in a timely manner may be prohibited from enrollment until data submission is current.

### 10.3 Source Documentation Requirements

All data that is entered in the eCRFs must have source documentation available in the patient medical records. Data to be collected for the study purposes must not be entered directly onto eCRFs. The data must be recorded from original source documents and available for review by the study monitor. Regulations require that Investigators maintain information in the study patient's medical records that corroborate data collected on the eCRFs. The source documentation may consist of, but is not limited to: operative or procedure reports, progress notes, discharge summaries, laboratory reports, radiographic reports, medication logs, and worksheets. Source documents may be in electronic form and/or hard (paper) copies. Data recorded directly on CRFs such as patient-reported questionnaires or other data are deemed acceptable for collection outside of the EDC.

Protocol deviation information can be recorded directly on the protocol deviation eCRF.

### 10.4 Quality Control and Assurance Procedures

Because of the potential for errors and inaccuracies in entering data into eCRFs, originals or photocopies of all relevant procedural records and reports, post-procedural examinations, laboratory and other test results may be kept on file in the Investigator's patient study files. Access to eCRFs and copies of test results must be available at all times for inspection by the study monitor.

All clinical sites will be audited periodically by a study monitor employed or contracted by the Sponsor for protocol adherence, accuracy of eCRFs, and compliance to applicable regulations. Evident patterns of non-compliance with respect to these standards will be cause for the site to be put on probation for a period of one month. If corrective actions are not subsequently undertaken, the clinical site will be asked to withdraw.

The Sponsor will provide data management through a secure, password protected EDC system accessible via the Internet. Passwords will be issued to appropriate data management personnel to ensure confidentiality and protection of the data by allowing variable levels of access to the computer system.

## 11 ADVERSE EVENT REPORTING AND ASSESSMENTS

Adverse events will be captured for all study patients from the time of enrollment until the patient's participation has ended (i.e. completion of study or withdrawal of consent).

## 11.1 Definitions

### 11.1.1 Adverse Event

An Adverse Event (AE) is any untoward medical occurrence, unintended disease or injury, or untoward clinical signs (including abnormal laboratory findings) in patients, users, or other persons, whether or not related to the investigational medical device.

### 11.1.2 Serious Adverse Event

A serious adverse event (SAE) is an adverse event that:

- Results in death
- Is life-threatening
- Requires inpatient hospitalization or prolongation of existing hospitalization
- Results in persistent or significant disability/incapacity, or
- Is an important medical event which may jeopardize the patient, and may require medical or surgical intervention to prevent one of the above outcomes

A planned hospitalization for a pre-existing condition, or a procedure required by the clinical investigation plan (CIP), without a serious deterioration in health, is not considered a serious adverse event.

### 11.1.3 Anticipated Adverse Events

Anticipated adverse events are AEs that have been identified in the CIP, IFU, and informed consent as possible adverse events.

### 11.1.4 Unanticipated Adverse Device Effect (UADE)

Unanticipated adverse device effect (UADE) is any serious adverse effect on health or safety or any life-threatening problem or death caused by, or associated with, a device, if that effect, problem, or death was not previously identified in nature, severity, or degree of incidence in the investigational plan or application (including a supplementary plan or application), or any other unanticipated serious problem associated with a device that relates to the rights, safety, or welfare of patients.

## 11.2 AE Reporting Requirements

The Investigator will report all adverse events to the Sponsor as soon as possible, but no later than 10 working days after the Investigator first learns of the event.

Each adverse event must be reported on a separate AE CRF. In the event that the EDC system is not in service or otherwise not accessible, the Sponsor must be notified by email [REDACTED]. The AE CRF should be completed as soon as possible thereafter.

At the time of initial notification, the following minimal information must be provided:

- Study site number
- Patient ID number
- Site's awareness date
- AE description
- Causal relationship to device and implant procedure, if known

The site will provide the Sponsor copies of relevant supporting source documentation (e.g. admission H&P, implant procedure report, discharge summary, echocardiogram and laboratory results) for all adverse events requiring CEC adjudication (at a minimum, safety endpoints) and those events determined by the Sponsor to require additional investigation.

Adverse events must be followed until resolution, the patient is lost to follow-up, the patient has withdrawn consent, or the adverse event is otherwise explained.

The Investigator will inform their IRB and FDA of adverse events in accordance with the relevant local and regional regulatory requirements.

### 11.3 Findings That Do Not Require Reporting to the Sponsor

For purposes of this study, the following findings are not considered adverse events requiring reporting to the Sponsor. These findings are normally expected to occur in association with treatment of tricuspid regurgitation, and/or are associated with customary, standard care of patients undergoing transcatheter, cardiovascular procedures.

- Post-procedure pain (within 48 hour of procedure) not requiring treatment or treated with non-opioids
- Abnormal or out of range lab values (e.g. electrolyte imbalance) that are not clinically significant and do not require correction or treatment.

**Note:** Abnormal lab values that roll up to a diagnosis should not be reported as separate AEs (e.g. elevated BNP in patient with heart failure; increased K+ in patient with renal insufficiency; elevated white blood count without signs or symptoms of infection).

- Low grade temperature increase without signs and symptoms of infection
- Minor, localized tenderness, swelling, induration, oozing, etc. at access site(s)
- Sinus bradycardia or tachycardia that does not require treatment or intervention
- Systolic or diastolic blood pressure changes that do not require treatment or intervention
- The need for insulin in a diabetic patient in the post op period

This list of findings is intended to provide guidance to the study sites for the purpose of adverse event reporting. The Investigator should utilize his/her own clinical judgment in evaluating adverse experiences, and may decide that the above findings should be reported as adverse events.

#### 11.4 Pre-Existing Conditions

Pre-existing medical conditions or symptoms reported prior to patient enrollment will not be recorded as an AE. In the event there is a worsening in the pre-existing medical condition or symptoms due to the device, implant procedure, or study-related procedures, then an AE must be recorded.

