## 5 FEASIBILITY ENDPOINTS

### 5.1 Safety Endpoint

Safety will be analyzed as a composite endpoint of Major Adverse Events (MAEs) at 30 days which includes:

- Cardiovascular mortality
- Myocardial infarction (MI)
- Stroke
- Renal complications requiring unplanned dialysis or renal replacement therapy
- Severe bleeding\*
- Unplanned or emergency re-intervention (either percutaneous or surgical) related to the device
- Major access site and vascular complications requiring intervention

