## 11.7 Sponsor Assessment and Reporting

The Sponsor is responsible for the classification and reporting of adverse events and ongoing safety evaluation of the clinical investigation in accordance with 21 CFR 812.

All AEs will be reviewed by the Sponsor's Clinical Safety department. Each AE will be assessed for seriousness, device and procedure relatedness, and whether it was anticipated or not anticipated (based on the list of potential risks provided in section 3.1). In case of disagreement between the Sponsor or CEC and the Investigator, the Sponsor will communicate both opinions to concerned parties, as necessary.

A summary of adverse events will be reported to the FDA annually in the Annual Progress Report (APR).

The Sponsor will also report any confirmed unanticipated adverse device effect (UADE) to FDA as soon as possible, but no later than 10 working days after first receiving notice of the effect.

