### **14.2 Clinical Events Committee (CEC)**

The Clinical Events Committee is responsible for reviewing and adjudicating specified individual adverse events over the course of the study. CEC activities, including roles and responsibilities, procedures, and definitions will be defined in the CEC Charter.

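### Protocol section 11.4 makes AE recording of a worsened pre-existing condition depend on cause, contradicting the AE definition and leaving AE/SAE data, and possibly the 30-day MAE rate, open to undercounting

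*Protocol*

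**What the plan says.** Section 11.4 of the protocol has two sentences. The first is an exclusion: "Pre-existing medical conditions or symptoms reported prior to patient enrollment will not be recorded as an AE". The second brings worsening back in, with a causal condition attached: "In the event there is a worsening in the pre-existing medical condition or symptoms due to the device, implant procedure, or study-related procedures", an AE has to be recorded. Worsening from any other cause is not mentioned.

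The rest of section 11 is written differently. The AE definition in 11.1.1 covers any untoward occurrence "whether or not related to the investigational medical device". Section 11.2 states: "The Investigator will report all adverse events to the Sponsor as soon as possible". Section 11.5 then grades the relationship of each AE to device and procedure in five categories, one of which is not related.

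The later safety steps act on AEs. In 11.7, "All AEs will be reviewed by the Sponsor's Clinical Safety department". Under 11.2, sites send supporting source documents "for all adverse events requiring CEC adjudication (at a minimum, safety endpoints"), and under 14.2 the CEC is "responsible for reviewing and adjudicating specified individual adverse events over the course of the study". Section 12.4.1 bases the MAE analysis on adjudicated data.

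The MAE list in 5.1 includes "Renal complications requiring unplanned dialysis or renal replacement therapy", with no requirement that the event be related to the device or procedure. Re-intervention is the only component that carries such a requirement.

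**The concern.** Section 11.4 places a yes/no causality judgement at the site ahead of the protocol's own causality system. It does not say whether a relationship graded unlikely or possible would count as being due to the device or procedure. Section 11.5 tells investigators to weigh the natural history of the underlying disease, and in this population that is the obvious alternative explanation: every patient enters with symptomatic severe TR.

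The study is single-arm and describes no blinding of the investigator. With no control group, the absolute event rates are the safety evidence. An omitted event can only lower those rates, so any error favours the device. With up to 30 sites, some may follow 11.4 and others 11.1.1, and reporting would then differ by site for reasons unrelated to patient risk.

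**Working it through.** The plan gives no expected event rate, power or margin for the safety endpoint (12.4.1 rules out hypothesis testing), so there is no stated figure to reproduce. The check is a comparison of texts, followed by the arithmetic of one lost event.

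**1. Is there a contradiction?** Under 11.1.1 an unrelated deterioration is an AE. Under 11.4 a pre-existing condition is not an AE, and its deterioration is brought back in only by a clause about cause. If every deterioration were recordable anyway, that clause would do no work. The duty in 11.2 does not settle the matter, because it depends on what counts as an AE, which 11.4 narrows.

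**2. Which outcomes are exposed?**
- *Dialysis (MAE):* exposed. Exclusion criterion 18 removes chronic dialysis and eGFR of 30 or below, so patients with eGFR above 30 and renal disease are eligible. No relatedness condition applies, and no separate reporting rule was found.
- *Severe bleeding (MAE):* largely protected. The bleeding definition in Appendix A requires all overt bleeding after the procedure to be reported, whatever its cause.
- *Death (MAE if cardiovascular):* protected. Appendix A classifies every death and counts it as cardiovascular unless it is unequivocally not.
- *Access-site complications and re-intervention (MAE):* device- or procedure-linked by nature, so 11.4 itself calls for an AE.
- *MI and stroke (MAE):* defined as new acute events, so 11.4 is unlikely to be applied to them.
- *Heart failure:* not an MAE component. Hospitalizations are a separate endpoint and are asked about at follow-up visits (Table 9). The exposure is mainly in the AE/SAE listings (protocol 12.6) and the early and late AE percentages (SAP 9.2).

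**3. What does one lost MAE do?** Inputs: n = 65, the enrollment cap in 12.1; 95% Clopper-Pearson intervals, SAP 6.1. The patient must have no other MAE by day 30; otherwise the composite is unchanged.

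Change per lost event = 1/65 = 1.5 percentage points.

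Interval for x events: lower limit = 2.5th percentile of Beta(x, n−x+1); upper limit = 97.5th percentile of Beta(x+1, n−x).

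The documents give no event count, so six true MAEs is an assumption made for illustration:

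| MAEs recorded | Rate | 95% CI |
|---|---|---|
| 6 (none lost) | 9.2% | 3.5 to 19.0 |
| 5 (one lost) | 7.7% | 2.5 to 17.0 |
| 4 (two lost) | 6.2% | 1.7 to 15.0 |
| 3 (three lost) | 4.6% | 1.0 to 12.9 |

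Each lost event also lowers the upper limit by about 2 points. Clinical success (5.2.3) is procedural success with no MAE at 30 days, so a patient who met procedural success and whose only MAE was lost would be counted as a success.

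**4. Is the cut-off for pre-existing clear?** No. Section 11.4 uses enrollment, which 8.4 sets at skin incision. Appendix A uses screening. A condition that arises between the two is pre-existing under one text and not under the other.

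**The case against.** The strongest reply is that 11.4 never says only. It says when an AE must be recorded and does not forbid recording the rest. Section 11.1.1 is causality-neutral, 11.2 covers all AEs, and 3.1 promises that all safety events will be collected. The SAE definition in 11.1.2 exempts planned admissions for a pre-existing condition unless health has seriously deteriorated, which implies that serious deterioration can be an SAE, with no causality test. Starting dialysis in a patient not previously on it can also be read as a new occurrence. Soon after a procedure, a not-related judgement is harder to defend, and 11.5 sends unassessable cases to possible.

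Much of this stands. A reader might infer a settled rule that only related worsening is recorded; the documents do not support that, because other sections say the opposite. The defect is a contradiction that permits omission.

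A reader might also infer that bleeding and heart-failure events are kept out of the safety endpoint. That does not follow, given the bleeding reporting rule and the absence of heart failure from the MAE list.

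Nor can it be said that an omitted event never reaches the CEC. The CEC Charter overrides the protocol where they disagree (Appendix A) and may set other triggers. Laboratory tests and hospitalization questions at 30 days, together with source checks under 13.1, may bring an event to light.

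What remains is that 11.4 is the specific text a site will consult when a known condition deteriorates. Monitoring is a limited safeguard, since an unrecorded deterioration judged unrelated complies with 11.4 and may give the monitor nothing to query.

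**Conclusion.** Section 11.4 is wrong as written. It contradicts 11.1.1 and 11.2, and a site that follows it can leave deterioration it judges unrelated out of the AE/SAE data before anyone else assesses it. Any resulting error lowers the counts.

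For the 30-day MAE the demonstrable exposure is narrow: mainly new dialysis in patients with baseline renal disease. The size is 1.5 points per lost event at n = 65, under the conditions given above, and more if fewer patients are enrolled. How many events would be lost cannot be estimated. That would need the frequency of such events, the share judged unrelated and the share recovered by other routes, and the documents give none of these. The table shows sensitivity to an assumed count and is not a forecast.

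**What to change.** 1. Reword 11.4 along these lines: any worsening of a pre-existing condition, in severity or frequency, after AE collection has started is recorded as an AE regardless of cause; its relationship to device and procedure is then assessed under 11.5.
2. State in 11.2 or 14.2 that any event that may meet an MAE component goes to the CEC irrespective of the investigator's view of causality, and check that the CEC Charter agrees.
3. Choose one cut-off for pre-existing and use it in both 11.4 and Appendix A.

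The cost is a short amendment and a notice to sites, with no new visits or tests. Sites will enter more AEs, and the reported AE and MAE rates may look slightly less favourable.

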#### 11.5 Investigator AE Causality Assessment

Adverse events will be assessed by the Investigator for causality to the study device and index procedure. The relationship between the use of the study device and study/implant procedure and the occurrence of each adverse event will be assessed and categorized.

During causality assessment, clinical judgement shall be used and the relevant study documents (i.e. CIP, ICF, IFU and/or CIB) shall be consulted for the listing of foreseeable adverse events/potential risks. The presence of confounding factors, such as concomitant medication/treatment, the natural history of the underlying disease, other concurrent illnesses or risk factors shall also be considered.

- **Not related:** There is no relationship between the event and the device or implant procedure.
- **Unlikely:** The relationship with the use of the device seems not relevant and/or the event can be reasonably explained by another cause, but additional information may be obtained.
- **Possible:** The relationship with the use of the device is weak but cannot be ruled out completely. Alternative causes are also possible (e.g. an underlying or concurrent illness/ clinical condition or/and an effect of another device, drug or treatment). Cases

were relatedness cannot be assessed or no information has been obtained should also be classified as possible.

- **Probable:** The relationship with the use of the device seems relevant and/or the event cannot reasonably explained by another cause, but additional information may be obtained.
- **Related (Causal relationship):** The event is related to the device and/or procedure beyond a reasonable doubt.

\*Reference **Appendix A: Study Definitions** for the full causality definitions.

An adverse event can be related both to the study procedure and the study device. Complications of procedures are considered not related if the said procedures would have been applied to the patients also in the absence of study device use/application.

In some particular cases the event may not be able to be not adequately assessed because information is insufficient or contradictory and/or the data cannot be verified or supplemented. The Sponsor and the Investigators will make the maximum effort to define and categorize the event and avoid these situations.

